# 8.3 Exploratory Efficacy Endpoint Analyses:

The following exploratory efficacy endpoints will be analysed using MMRM. For data that may not follow a normal distribution, we will consider either using an appropriate transformation to approximate normality or using the generalized linear model (e.g., for categorical outcomes) utilizing the generalized estimating equations or generalized linear mixed model with random intercept to address correlation of repeated measures from the same subject. Appropriate distribution based on the outcome will be chosen to fit the chosen model.

- Change from baseline in pre-and post-bronchodilator forced expiratory volume in 1 second (FEV1), forced vital capacity (FVC), FEV1/FVC (total and percent predicted), and maximal mid-expiratory flow at end of treatment. The analyses of this outcome will be dependent on the amount of spirometry data available.
- Change from baseline in St. George's Respiratory Questionnaire (SGRQ) (total and subscales), COPD Assessment Test (CAT), Modified Medical Research Council Questionnaire (MMRC), San Diego Breath Questionnaire (SOBQ) and daily symptom scores

Pearson (or Spearman rank) correlation of select biomarkers shown to be responsive to treatment with time-matched drug concentrations and PK parameters, if available, will be used to evaluate exposure-response relationship.

# 8.4 Analysis of Pharmacokinetics

Sparse PK sampling will be performed before and after study treatment dosing as detailed in the SoA and MOP. Blood samples of approximately 3 mL will be collected for measurement of blood concentrations of Alvelestat (MPH966) as specified in the SoA. Instructions for the

collection and handling of biological samples will be provided by the DCC. The actual date and time (24-hour clock time) of each sample willbe recorded.

# 8.5 Correlation of PK Exposure with Efficacy (PD) and Safety

Correlation of select biomarkers (shown to have significant treatment effect) with timematched drug concentrations and PK parameters, if available, may be used to evaluate exposure-response relationship.

The safety correlation analysis with drug concentration will be done for the safety parameters shown to be sensitive to Alvelestat exposure. The comparison of exposure will be done between groups with non-clinically significant changes and clinically significant changes in safety parameters using graphic and statistical methods where data allow.

# 8.5.1 Presentation of Concentration Data

# 8.5.1.1 Handling of Missing Data

Plasma concentrations below the lower limit of quantification (LLOQ) of the assay are designated as NQ (not quantifiable) in the PK data and will be replaced by half value of LLOQ in listings. Values above the ULOQ will be replaced by 1.5\*ULOQ. This approach will be used for non-PK data as well.

Samples taken far outside the sampling windows and any other protocol deviation related to plasma concentration measurements will be discussed but will be excluded from summary tables. Missing values due to bad sample or unable to measure will also be excluded for that visit. Other non-missing data from the same subject will be included in the analyses.

# 8.5.1.2 Listing, Presentation and Summary of PK Data

The following presentations of subject plasma concentration data will be provided for the Alvelestat (MPH966) treatment group for the PK Set:

- A listing including subject, week/time point treatment and plasma concentrations
- A summary table of plasma concentrations at each week/time point (n; Geometric mean, SD, coefficient of variation (CV)% calculated as 100% × SD/mean, minimum, median and maximum)
- A figure with individual visits 1 to 12 from pre-dose through 1-2h post-dose plasma concentration-time profiles on both linear and log-linear scale (Y-axis is the concentrations; X-axis is the time e.g. Weeks 1, 4, 8, 12)
- A figure with geometric mean ± SD plasma concentration-time profiles presented on both linear and log-linear scales (Y-axis is the Visit x pre dose ( or visit x 1-2 hours post dose concentrations – 2 separate plots; X-axis is the time e.g. Weeks 1, 4, 8, 12)

Nominal time points and visit number (planned) will be used for summary and geometric mean concentration graphical presentations. The time of collection of the pre-dose sample will be set to zero. Mean plasma concentrations will not be presented in the

summary or graphics for the time points with 50% or more of the actual values are below the LLOQ or missing.

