# 3.5.3 Sample Size

Over the course of the study, target enrolment is 66 with the goal of 60 completers. Participants will be randomized in a 1:1 ratio to receive one of the following: 120mg Alvelestat (MPH966) BID or placebo. Randomization will be stratified by AAT genotype/phenotype.

The study will be powered for within-individual change in plasma desmosine/isodesmosine (DES) as the primary endpoint at Week 12 compared to baseline. A sample size of 30 participants in the MPH966 treatment group will give us >90% power to detect a 15% mean decrease of plasma DES from baseline to 12 weeks follow-up in patients treated with MPH966 (within subject change) using a two-sided paired t-test at  $\alpha$ =0.05. The calculation is based on an assumed correlation value of 0.5, baseline mean DES value of 0.466 and standard deviation of 0.09. This 15% mean decrease has been observed in trials of standard dose augmentation versus placebo (Ma S, 2013). A recent study of double dose versus single dose augmentation revealed a within subject decrease in plasma DES from 0.42 +/-0.03 ng/ml to 0.38 +/- 0.03 ng/ml (Campos MA, 2019). We will have >99% power to detect a comparable difference in DES in those who have Alvelestat added to augmentation if we assume their observed SD=0.03 and 85% power if we double their assumed SD, i.e., SD=0.06. Power will not be enough (~50%) to detect this difference if we use our original SD value of 0.9.

For comparing the mean change in DES between the two groups (placebo vs. MPH966), and assuming that there is no placebo effect over 12 weeks, a two-sided two sample t-test at  $\alpha$ =0.05 with a sample size of 60 (30 per group) reveals that we will have 82% power to detect a 15% difference in mean change in plasma DES.

By including a 10% attrition rate over 12 weeks, the required sample size is inflated to 66 (33 per group) to achieve the estimated powers. If we observe attrition rate less than we expected, we will have more statistical power to detect the expected differences. As one interim analysis will be conducted only for safety concerns (see Data Safety and Monitoring Plan), no adjustments to the Type I error are considered for estimating statistical powers.

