Biomarker data are reported as concentration results, measured using a specific assay with a working range defined by the two limits: Lower limit of quantification (LLOQ) and Upper limit of quantification (ULOQ). Values which fall below the LLOQ or above the ULOQ are reported as <LLOQ \* dilution factor (dilution factor: if sample diluted and concentration measured still below LLOQ) and > ULOQ \* dilution factor, respectively. All results for the above biomarker parameters, if collected, will be summarised on the respective populations by descriptive statistics stratified by treatment and time-point, and including the geometric mean and coefficient of variation. Changes in the biomarker concentrations from baseline (Study Day 1 pre-dose) will be also summarised at each post-baseline time-point. In the summary table, the frequency (n, %) of values below the LLOQ and above the ULOQ, respectively, will be included. In case of values below the LLOQ and/or values above the ULOQ, the values, reported as <LLOQ will be imputed as 0.5\*LLOQ and values reported as >ULOQ will be imputed as 1.5\*ULOQ.

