	Individual plasma concentration Profiles for	PK Set
	Alvelestat (MPH966) vs Time by Treatment – Linear	
	Scale	
	Individual plasma concentration Profiles for	PK Set
	Alvelestat (MPH966) vs Time by Treatment – Log-	
	Linear Scale	
	Geometric Mean (± SD) plasma concentration	PK Set
	Profile for Alvelestat (MPH966) vs Time by	
	Treatment – Linear Scale	
	Geometric Mean (± SD) plasma concentration	PK Set
	Profile for Alvelestat (MPH966) vs Time by	
	Treatment – Log-Linear Scale	
	Box-plot of plasma concentration for Alvelestat	PK Set
	(MPH966) vs Time (pre-dose and by visit post-dose)	
	by Treatment	

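### The PK mean-profile figures put an additive SD around a geometric mean, so the lower error bar reaches too far down and, at high variability, cannot be drawn on the log axis

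*SAP*

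**What the plan says.** SAP Section 8.5.1.2 summarises plasma alvelestat concentrations by visit and time point with these statistics: "Geometric mean, SD, coefficient of variation (CV)% calculated as 100% × SD/mean, minimum, median and maximum". The only mean in that list is the geometric one. The section then plans "A figure with geometric mean ± SD plasma concentration-time profiles presented on both linear and log-linear scales". The list of figures in SAP Section 14.2 repeats this in two titles beginning "Geometric Mean (± SD) plasma concentration", one for a linear and one for a log-linear scale, so the pairing is a planned output and not a slip in one sentence.

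The SAP does not say whether the SD is arithmetic or geometric, and it defines no log-scale SD, geometric SD or geometric CV. Two neighbouring rules affect these displays. Values below the quantification limit "will be replaced by half value of LLOQ in listings" (Section 8.5.1.1), with no separate rule stated for PK summaries. Means are withheld only for "time points with 50% or more of the actual values are below the LLOQ or missing".

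**The concern.** A geometric mean is the centre of the data on the log scale. An error bar around it should be symmetric in ratio, not in concentration units. A plus-or-minus bar built from an ordinary SD takes its centre from one scale and its spread from another. A geometric SD has no units and cannot be added to or subtracted from a concentration in nM. Read literally, neither kind of SD gives a meaningful bar.

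This touches a question that readers of the PK section will have. Protocol Section 5.5 rests the dose on plasma levels above 300 nM, and Protocol Section 3.1 says that levels in earlier trials averaged 200 nM. A reader who compares the lower bar with 300 nM would see exposure falling further than the data show.

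**Working it through.** **Inputs.** The statistics and plot form come from SAP Sections 8.5.1.2 and 14.2. The documents give no figure for PK variability, so the log-scale SD, *s*, is an assumption shown over a range. The SAP states no numerical result on this point, so there is none to reproduce.

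**Formulas** (log-normal concentrations, GM = 1):
- arithmetic SD = exp(s²/2) × √(exp(s²) − 1)
- arithmetic CV = √(exp(s²) − 1)
- bar as written, with the SD read as arithmetic: 1 − SD to 1 + SD
- multiplicative interval: exp(−s) to exp(s), that is GM/GSD to GM×GSD with GSD = exp(s)

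**Worked case, s = 0.5.** exp(0.125) = 1.133 and √(exp(0.25) − 1) = √0.284 = 0.533, so SD = 1.133 × 0.533 = 0.604. The bar is 0.40 to 1.60. The multiplicative interval is 0.61 to 1.65.

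| s | CV | SD | Bar as written | GM/GSD to GM×GSD |
|---|---|---|---|---|
| 0.294 | 30% | 0.313 | 0.69 to 1.31 | 0.75 to 1.34 |
| 0.5 | 53% | 0.604 | 0.40 to 1.60 | 0.61 to 1.65 |
| 0.6 | 66% | 0.788 | 0.21 to 1.79 | 0.55 to 1.82 |
| 0.7 | 80% | 1.016 | −0.02 to 2.02 | 0.50 to 2.01 |
| 0.833 | 100% | 1.414 | −0.41 to 2.41 | 0.43 to 2.30 |

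The upper limits barely differ until variability is high; the error is mostly in the lower limit. The bars as written cover 72% of the distribution at CV 30% and 79% at CV 50%, against 68% for the multiplicative interval.

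**Where the lower bar reaches zero.** This needs SD ≥ GM, that is exp(s²) × (exp(s²) − 1) ≥ 1. With x = exp(s²), x² − x − 1 = 0 gives x = 1.618, so s = √ln(1.618) = 0.694 and CV = √0.618 = 78.6%.

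**Chance in a sample.** SAP Section 3.5.3 plans on "A sample size of 30 participants in the MPH966 treatment group". In 40,000 simulated samples of 30, the lower bar was zero or negative in 0.3% at CV 50%, 4% at 60%, 16% at 70%, 36% at 80% and 74% at 100%. Values below the limit can raise this. Suppose they enter the summaries as half the limit and the quantifiable values have CV 50% and a median of five times the limit. The chance is then 10% with 10% of values below the limit, 48% with 20%, and 84% with 30%. All three shares are under the 50% rule, so with no other values missing these time points would still be plotted. These inputs are assumptions too.

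**Against 300 nM (illustration).** With an assumed GM of 500 nM and CV 50%, SD/GM is 0.559 and GSD is exp(0.472). The bar as written ends at 500 × 0.441 = about 220 nM. GM/GSD is 500 × 0.624 = 312 nM. The two fall on opposite sides of 300 nM.

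**The CV.** The table defines "coefficient of variation (CV)% calculated as 100% × SD/mean", but the only mean listed is geometric. With the arithmetic mean as denominator, the CV at s = 0.5 is 53%. With the geometric mean it is 0.604/1 = 60%. At s = 0.7 the two are 80% and 102%.

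**The case against.** The SAP never calls the SD arithmetic. That is inferred from the plus-or-minus form and the CV formula, so the text is better described as underspecified. A programmer might take the phrase as shorthand for bars computed on logs and back-transformed, which would be right. This stands as a caution, but nothing in the SAP directs anyone to do so, and the remedy is the same.

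Three stronger readings are tempting, and the documents do not support them.
- *The log-scale figure cannot be drawn.* That follows only at a CV of about 79% or more, or with a substantial share of values below the limit. The documents give neither. At CV 30% or less the bars can be drawn and differ modestly from the multiplicative interval.
- *The CV formula is wrong.* SD divided by the mean is the ordinary CV, and under log-normality its population value is √(exp(s²) − 1), the same as the geometric CV. SAP Section 6.1 lists the mean among its general continuous summaries, so an arithmetic denominator is a natural reading. Only the unnamed denominator remains as a fault.
- *The bars hide low exposure.* The direction is the opposite: they reach too low and make exposure look worse against 300 nM than it is.

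It is also fair to say that the plan offers better ways to judge exposure: the minimum, median and maximum in the same table, a listing of concentrations, individual profiles on both scales, and box-plots. None of these is affected.

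**Conclusion.** The point holds for the figures as written: an SD bar around a geometric mean is not a valid spread under either meaning of SD. If the SD is arithmetic and concentrations are log-normal, the lower limit is too low at every level of variability shown: 0.69 against 0.75 of the GM at CV 30%, and 0.40 against 0.61 at log-scale SD 0.5. Failure on the log axis is conditional on a log-scale SD of about 0.7 or more, or on enough values below the limit, and the documents do not show whether either will occur. The CV needs only its denominator named.

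The consequence is small. These are descriptive PK displays, and no test, power figure, primary endpoint or stated decision rule depends on them. The change is worth making because it is nearly free and removes a misleading comparison with 300 nM.

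**What to change.** Amend SAP Section 8.5.1.2 and the two geometric-mean figure titles in Section 14.2:
- Plot GM/GSD to GM×GSD on both scales, with GSD = exp(s) and s the SD of the log concentrations. These limits are always positive.
- In the summary table, list GSD and geometric CV = 100 × √(exp(s²) − 1) beside the geometric mean.
- If the arithmetic SD and CV are kept, list the arithmetic mean and name it as the CV denominator.
- State whether the half-limit substitution applies to PK summaries and figures as well as listings.
- Say which CV is meant for the biomarkers in SAP Section 6.1, where the summaries are described as "including the geometric mean and coefficient of variation".

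The cost is a few lines of SAP wording and a formula in the table and figure programs. Data collection, sample size and inference do not change.

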# 9 Safety Analyses

All analyses described in this section will be performed on the SAF and will be presented by treatment arm and overall. The results will be descriptive in nature. All data will be summarized and listed.

Safety will be assessed on the basis of exposure, compliance, AEs, laboratory parameters, vital signs and physical examination.

# 9.1 Extent of Exposure

The duration of exposure will be expressed as the time in days from the first dose of treatment through to last treatment day (inclusive). Duration of exposure will be summarized for the SAF using summary statistics for continuous variables.

### 9.2 Treatment Compliance

From baseline and at subsequent visits while the patient is being treated with the study treatment, the patient will be directed to bring back all unused tablets. Compliance will be checked by calculating number of pills taken/expected pills to be taken by the Investigator during those visits and recorded on the eCRF.

The number and percentage of compliant patients will be presented for the SAF by study visit, where compliant is defined as percentage compliance between 80.0% and 100.0% inclusive. The following percentage compliance categories will be presented:<80.0%;  $\geq$ 80.0% to  $\leq$ 100.0%; >100.0%. Descriptive statistics for treatment compliance will also be presented.

# 9.3 Safety Outcomes

### 9.3.1 Primary Safety Outcomes

The primary safety outcomes of interest are (1) numbers and % of subjects who experience at least 1 treatment-emergent adverse event and (2) adverse events of special interest (liver function abnormalities, corrected QT interval/cardiac, infections, and neutropenia). AEs will be coded using the Medical Dictionary for Regulatory Activities (MedDRA). Summaries will be by system organ class and preferred term. We will also present data separately by augmentation.

Treatment-emergent AEs (TEAEs) are defined as any AE occurring on or after the first dose of study medication. Listing will be sorted by treatment arm, subject ID, chronologically (start and end dates) and then alphabetically by SOC, PT and then verbatim description. The listing will include all the distinct levels of SOC, PT and the verbatim Investigator description reported in the study. A flag per subject will be included to indicate whether the patient received COVID-19 vaccination. If a participant experiences the same preferred term multiple times, the event will be counted only once overall and by the greatest severity. The frequency and incidence of TEAEs will be presented by system organ class and preferred term for each treatment group (number and percentage of participants experiencing at least 1 AE per preferred term as well as the number of observed events per preferred term). Separate tables will be presented by severity and by relationship to study drug. All AEs will be presented in a comprehensive listing

including participant number, treatment regimen, day of onset, severity, seriousness, action taken, outcome, relationship to treatment, onset/stop, and duration. Details of SAEs and AEs leading to withdrawal will be listed separately.

The frequency and incidence of adverse events of acute exacerbations of COPD will be presented (number and percentage of participants experiencing at least 1 AE per preferred term as well as the number of observed events per preferred term) and overall. Events that started after treatment initiation (TEAEs) up until Week 12 will only be presented, meaning that events commencing after the end of treatment and during the safety follow up period will not be summarized.

AESIs, including liver function abnormalities, ECG/cardiac events, infections, and neutropenia, will be tabulated and summarized by treatment group and overall.

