## 2. Schedule of Activities (SOA)

Visit #	Visit 1	Visit 2	Visit 3	Visit 4	Visit 5	Visit 6	Visit 7	Visit 8	Visit 9	Visit 10	Visit 11	Visit 12
Visit Description	Pre-bronch/Screen	Baseline bronch	Randomize	Safety F/U	Safety F/U	4 week F/U	Safety F/U	8 week F/U	Safety F/U and Pre-bronch	End of study bronch	Study End	Washout End
Week (from randomization)	-4 to 0	-1	0	+1	+2	+4	+6	+8	+10	+11	+12	+16
Randomization			X									
Baseline history	X											
Physical exam	X	X	X	X	X	X	X	X	X	X	X	X
Interim history and adverse event recording		X	X	X	X	X	X	X	X	X	X	X
Blood draw (routine/safety)	X			X	X	X	X	X	X		X	X
Blood draw (biomarkers)	X		X			X		X			X	X
Blood (PK)			X@	X	X	X		X	X		X	
Pregnancy test	X		X	X	X	X	X	X	X		X	X
ECG	X		X@	X	X	X		X	X		X	X
Sputum biomarkers	X										X	
Spiro- pre and post BD			X			X					X	X
Spiro – post BD	X								X			
PROs#			X			X					X	X
Bronchoscopy		X								X		
Phone contact		X (day after)								X (day after)		
Electronic diary	X		X	X	X	X	X	X	X	X	X	X

#Patient reported outcomes to include Modified Medical Research Council questionnaire (MMRC), COPD assessment test (CAT), St George Respiratory Questionnaire (SGRQ), San Diego Shortness of Breath Questionnaire; @ pre-dose and between 1 and 2 hours post-dose

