### 6.4. Screen Failures

Screen failures are defined as participants who consent to participate in the clinical study but are not subsequently randomized. A minimal set of screen failure information is required to ensure transparent reporting of screen failure participants to meet the Consolidated Standards of Reporting Trials (CONSORT) publishing requirements and to respond to queries from regulatory authorities. Minimal information includes demography, screen failure details, available eligibility criteria, and any SAEs. Individuals who do not meet the criteria for participation in this study (screen failures) may be rescreened after discussion with and approval by the Data Coordinating Center (DCC) and/or Principal Investigator (PI).

The **screening period may be extended beyond 28 days** in the following circumstances after discussion with and approval of the DCC and/or PI:

- All screening inclusion/exclusion criteria are met but the participant's schedule, including genetic testing, prevented randomization within the screening period.
- The participant experiences an acute exacerbation of COPD during the screening period.

Additionally, individual laboratory parameters or screening tests may be repeated, within the screening period, if the result is considered aberrant or not clinically consistent with the patient's health status. Decisions to re-test should be made in conjunction with the study PI.

Participants who have individual laboratory parameters re-tested should have the results entered in the electronic case report form (eCRF).

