### 9.4.1. Time Period and Frequency for Collecting AE and SAE Information

All AEs and SAEs will be collected from the signing of the ICF until the follow-up visit at the time points specified in the SoA.

All SAEs will be recorded and reported to the DCC within 24 hours, as indicated in [Appendix 4](#).

The method of recording, evaluating, and assessing causality of AEs and SAEs and the procedures for completing and transmitting SAE reports are provided in [Appendix 4](#).

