### 10.3.2. Safety Analyses

All safety analyses will be performed on the Safety Set.

Endpoint	Statistical Analysis Methods
Primary	
AEs will be coded using the Medical Dictionary for Regulatory Activities (MedDRA). Summaries will be by system organ class and preferred term. Treatment-emergent AEs are defined as any AE occurring or worsening on or after the first dose of study medication. If a participant experiences the same preferred term multiple times, the event will be counted only once overall and by the greatest severity.
 
The frequency and incidence of treatment-emergent AEs will be presented by system organ class and preferred term for each treatment group (number and percentage of participants experiencing at least 1 AE per preferred term as well as the number of observed events per preferred term). Separate tables will be presented by severity and by relationship. All AEs will be presented in full in a comprehensive listing including participant number, treatment regimen, severity, seriousness, action taken, outcome, relationship to treatment, onset/stop, and duration. Details of SAEs and AEs leading to withdrawal will be listed separately.
 
Adverse Events of Special Interest AESIs, including liver function abnormalities, ECG/cardiac events, infections, and neutropenia, will be tabulated and summarized by treatment group and overall.

Secondary	Vital Signs

Endpoint	Statistical Analysis Methods

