# 10 Changes from Analysis Planned in the Protocol

In Version 1.3 of the protocol, augmentation therapy was removed from the list of not allowed treatment. Sample size calculation was revised but sample size remained the same. Also, stratified analyses by augmentation therapy will be performed.

Due to the risk during the COVID pandemic, spirometry as well as sputum and BAL collections were changed to optional. Consequently, all analyses using spirometry, sputum biomarkers, and BAL biomarker outcomes and data will no longer be performed in this study.

Primary analysis in the protocol is based on ANCOVA with outcome being the percent change at Week 12 from baseline. However, to minimize the effect of missing data and to maximize the information from all visits, the primary analysis is now based on fitting a mixed model using change from baseline at all available follow-up visits as outcome with the assumption of missing at random for missing data.

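### The SAP's definition of a treatment-emergent AE omits the protocol's worsening limb without declaring it, so an AE that begins before first dose and worsens on treatment could fall out of a primary safety count

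*SAP*

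**What the plan says.** The protocol's safety analysis section (10.3.2) gives this definition: "Treatment-emergent AEs are defined as any AE occurring or worsening on or after the first dose of study medication". SAP 9.3.1 gives nearly the same sentence without the worsening limb: "Treatment-emergent AEs (TEAEs) are defined as any AE occurring on or after the first dose of study medication". The key definitions in SAP 6.2 do not define the term, so nothing there restores the limb.

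Later in SAP 9.3.1, the paragraph on COPD exacerbations describes TEAEs by their start: "Events that started after treatment initiation (TEAEs) up until Week 12 will only be presented".

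SAP Section 10, headed "Changes from Analysis Planned in the Protocol", covers augmentation therapy and the sample size calculation, the optional spirometry, sputum and BAL collections, and the move from ANCOVA to a mixed model. It does not mention the TEAE definition.

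The number and percentage of subjects with one or more TEAEs is a primary safety endpoint in Protocol Section 4 and SAP 4.2.

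**The concern.** The two documents define one primary safety endpoint differently, and the SAP is the document a programmer will follow. An on-or-after-first-dose rule with no worsening limb is naturally coded as a comparison of onset date with first-dose date. An AE already on file at first dose then cannot become treatment-emergent, however much it worsens.

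At stake are the primary TEAE count and the tables and listings restricted to TEAEs, including those for serious events, withdrawals from study drug and maximum intensity. A pre-dose AE that became serious on treatment could appear instead in the SAP 14.3 listing of SAEs that are not treatment-emergent. Worsening of something already present is one of the ways a drug effect can show itself, which is why the protocol's extra limb matters.

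**Working it through.** The documents state no figure to reproduce, so the check is mainly a comparison of texts.

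**Step 1: can the exposed event exist?** Yes. Protocol 9.4.1 sets the start of collection: "All AEs and SAEs will be collected from the signing of the ICF". In the Schedule of Activities, the row "Interim history and adverse event recording" is first marked at Visit 2 (Week -1), where the optional baseline bronchoscopy also falls. Screening lasts up to 4 weeks, and Protocol 6.4 adds that the "screening period may be extended beyond 28 days" in stated circumstances, one of which is a COPD exacerbation during screening. AEs with onset before first dose can therefore be on file.

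**Step 2: how does each rule classify an AE?**

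| AE | Protocol 10.3.2 | SAP 9.3.1, by onset date |
|---|---|---|
| Starts on or after first dose | TEAE | TEAE |
| Starts after consent and before first dose, does not worsen | not TEAE | not TEAE |
| Starts after consent and before first dose, worsens on treatment, kept in one record | TEAE | **not TEAE** |
| Same, but the worsening is entered as a new AE | TEAE | TEAE |

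The rules differ only in the third row. A mild headache recorded in screening that becomes severe on treatment, updated in the same record, is an example.

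**Step 3: does any rule move the third row into the fourth?** None found. Appendix 4 makes an increase in frequency or intensity of a pre-existing condition an AE, but does not say that worsening of an AE already recorded opens a new entry. Its follow-up section sends updated information to the CRF first completed.

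**Step 4: which displays depend on the rule?** Counting titles in SAP Section 14 that name TEAEs:
- Tables, 6: all TEAEs, related, serious, related serious, leading to withdrawal of study drug, and maximum intensity.
- Listings, 4: serious, leading to withdrawal of study drug, headache, and COPD or its exacerbation.
- Total: 6 + 4 = 10.

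The AESI table is not limited to TEAEs by its title, so that endpoint need not be affected.

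**Step 5: what is one missed subject worth?** SAP 3.5.3 plans 33 randomized per arm and 30 completers per arm. One subject is 1/33 = 3.0 percentage points, or 1/30 = 3.3. The percentage moves only if the missed event is that subject's sole TEAE. Event-level tables can lose the event in any case.

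The documents give no rate for AEs that start in screening and worsen on treatment, so the expected number missed cannot be computed.

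**The case against.** The strongest reply is that Appendix 4 already does the work. It makes worsening of a pre-existing condition an AE, it excludes only fluctuations of conditions present or detected at study start that do not worsen, and its general definition speaks of subjects who have been given the product. On that reading a screening-period event is pre-existing at first dose, its worsening is a new AE, and the SAP wording captures it. This narrows the gap: a condition present before consent that worsens on treatment should still be counted, and some sites may treat screening events the same way. It does not close the gap. AEs are collected from consent, and nothing requires a new record for one already on file.

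Three further points have force:
- The COPD sentence is weak support for an onset-date reading. It limits one display, and its own explanation shows that it aims to exclude events starting after treatment ends.
- The event is not lost. The all-AE listing shows "day of onset, severity, seriousness, action taken, outcome, relationship to treatment, onset/stop, and duration". Those fields include no date of worsening, but they describe what is displayed and do not prove that the CRF fails to collect one.
- Whether a worsening stays in the original record depends on the eCRF and its completion guidelines, which are not among the documents.

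A reader might infer that the trial will undercount TEAEs, or that the comparison between arms is biased. The documents support neither claim. They show a narrower rule that could miss events. They do not show that events are missed, how many, or in which arm.

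**Conclusion.** The discrepancy is certain. For a primary safety endpoint the SAP states a narrower rule than the protocol and does not declare it. The consequence is conditional: an event is missed only if it starts between consent and first dose, worsens on treatment, stays in one record, and is classified by onset date. Its size cannot be computed from the documents and is probably small. SAP Section 9 makes the safety results descriptive, so the risk is an undercount and not a wrong test result. The change is worth making because the endpoint is primary and the correction is cheap.

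**What to change.** Restore *or worsening* to the TEAE definition in SAP 9.3.1. Before unblinding, add a derived flag that classes as TEAEs those AEs with onset before first dose that worsen on or after it. The SAP should say how worsening is judged and dated. An increase in severity on the Appendix 4 scale is the minimum; the protocol says only that the AE worsens, so adding frequency or seriousness would be a further choice for the sponsor. If the narrower rule is intended, declare and justify it in SAP Section 10.

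The cost is a wording change, one derived variable and possibly site queries for AEs still ongoing at first dose, to establish whether and when they worsened. No new assessments are needed.
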